7.4.8 Analysis of Other Safety Variables

For both Part A and Part B, all other safety data will be listed.

7.5 Pharmacokinetic Analyses

PK analyses will be performed based on the PK Analysis Set. All PK summaries will be presented by dose level of ALN-GO1. For Part B, the PK data of ALN-GO1 from both the blinded and open-label portion will be combined at each dose level.

Plasma and urine PK concentration data of ALN-GO1 will be summarized at each scheduled time point by dose level using descriptive statistics (n, mean, standard deviation [SD], standard error [SE], minimum, maximum, median, and percent coefficient of variation [%CV]). Mean plasma concentrations of ALN-GO1 versus nominal time will be plotted by dose level and study day on both linear scale and semi-logarithm scale. Individual plasma concentration versus actual time plots will also be provided. Individual and mean plasma concentrations of ALN-GO1 versus nominal time will also be plotted by dose level, study day and ADA status on both linear scale and semi-logarithm scale.

The plasma PK parameters and urine PK parameters of ALN-GO1 following single dose on Day 1 in Part A, single dose on Day 1 relative to ALN-GO1 dosing (Part B monthly and quarterly cohorts), multiple doses on Day 57 relative to ALN-GO1 dosing (Part B monthly cohorts only), and multiple doses on Day 85 relative to ALN-GO1 dosing (Part B quarterly cohorts only) will be summarized by regimen and ascending dose level. Geometric mean and geometric coefficient of variation will be added to the descriptive statistics for calculated PK parameters.

All individual subject plasma and urine concentrations data and actual sampling times will be listed. All PK parameters will be listed by subject, dose level, study day and ADA status.

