4.2.1 Safety Analysis Set

For both Part A and Part B, the Safety Analysis Set will include all subjects who received at least 1 dose of study drug (placebo or ALN-GO1).

The Safety Analysis Set will be used for safety analyses. Subjects will be summarized according to the treatment actually administered.

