4.3 General Statistical Considerations

The primary goal of the study is to evaluate the safety and tolerability of ALN-GO1 in healthy adult subjects and patients diagnosed with PH1. The data cutoff date for the primary analysis will occur after all subjects have either discontinued the study or completed all safety follow-up assessments (as in Section 3.2).

Continuous data will be described using descriptive statistics including the number of observations (n), mean, standard deviation, median, minimum, and maximum. Categorical and ordinal data will be described using the subject/patient count and percentage in each category. For the summary statistics of all numerical variables unless otherwise specified, minimum and maximum will be displayed to the same level of precision as reported. Mean, median, and standard deviation will be displayed to one level of precision greater than the data collected. Summary tables will present results by cohort for each ALN-GO1 dose in ascending dose order, total (all subjects receiving ALN-GO1), and placebo, where the placebo subjects/patients will be

combined across dose cohorts. Data will be displayed in all listings sorted by study part and cohorts with placebo ordered last.

Subjects/patients will be identified in the listings by the subject/patient identification number concatenated with the investigator number.

When count data are presented, the percentage will not be presented when the count is zero in order to draw attention to non-zero counts. A row denoted "Missing" will be included in tabulations where specified on the shells to account for dropouts and missing values. The denominator for all percentages will be the number of non-missing values in that cohort/treatment, unless otherwise specified.

If the assessment date is after the date of first study drug dose The study day will be calculated as:

Study day = Date of assessment – date of first dose of study drug + 1,

otherwise if assessment date is before the date of the first dose of study drug then study day will be calculated as:

Study day = Date of assessment - date of first study drug dose.

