6.2.2 PK Parameters

In Part A, PK parameters following single dose of ALN-GO1 (Day 1) will be characterized. In Part B, PK parameters following single and multiple doses (Day 1 and Day 57 for monthly dosing cohorts; Day 1 and Day 85 for quarterly dose cohorts) of ALN-GO1 will be calculated.

The following PK parameters will be calculated from the individual plasma concentration profiles ALN-GO1 by standard non-compartmental methods:

Parameters	Units	Description
C_{max}	ng/mL	Maximum observed plasma concentration
t_{max}	h	The time to reach the maximum observed concentration
AUC ₀₋₂₄	ng·h/mL	The area under the plasma concentration versus time curve, from time 0 to the 24 hour concentration (C_{24h}), as calculated by the linear trapezoidal method
AUC _{0-last}	ng·h/mL	The area under the plasma concentration versus time curve, from time 0 to t _{last} (time of last quantifiable concentration) as calculated by the linear trapezoidal method.
AUC _{0-inf}	ng·h/mL	The area under the plasma concentration versus time curve, from time 0 extrapolated to infinity, calculated as: $AUC_{0-inf} = AUC_{0-last} + C_{last}/\lambda z$ (Reported for Part A only)
AUC _{tau,ss}	ng·h/mL	Steady state area under the plasma concentration versus time curve, over the dosing interval at steady state (Reported for Part B only)
Lambda z (λ_Z)	h ⁻¹	Apparent terminal elimination rate constant calculated by linear regression of the terminal linear portion of the log concentration versus time curve
t _{1/2}	h	Apparent terminal elimination half-life, calculated as: $ln(2)/\lambda_Z$
CL/F	L/h	Total apparent body clearance after extravascular administration, calculated as: Dose/AUC _{0-inf}
CL/Fss	L/h	Total apparent body clearance at steady-state after extravascular administration, calculated as: Dose/AUC _{0-tau} (Reported for Part A only)
V _Z /F	L	Apparent volume of distribution based on the terminal elimination phase, calculated as: Dose/(AUC _{0-inf} × λ_Z) (for Part A) or Dose/(AUC _{0-tau} × λ_Z) (for Part B)

The following urine PK parameters will also be calculated:

Parameters	Units	Description
A _{e(0-24)}	mg	Cumulative amount of drug excreted in urine after dosing, calculated as the sum of $(C_{ur} \times V_{ur})$, where C_{ur} is the concentration in urine and V_{ur} is the volume of urine collected.
fe/F	%	Fraction eliminated in the urine, calculated as $(A_{e(0\text{-}24)}/Dose) \times 100$
CL_R	L/h	Renal clearance, calculated as A _{e(0-24)} /AUC ₀₋₂₄

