7.2 Analysis Periods and By-visit Data Presentation in Part B

Part B is the multiple ascending dose study part including monthly and quarterly dosing regimens with ALN-GO1 or placebo. Analysis periods and treatment groups will be defined in Section 7.2.1 and Section 7.2.2.

All data listings will be presented with corresponding treatment, study day relative to first dose date of study drug, and study day relative to first dose of ALN-GO1.

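### Part B concentration displays in SAP 7.5 use a day count that starts at placebo for crossover patients, so dose number is mislabelled and the groups do not match the PK parameter summaries

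*SAP*

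**What the plan says.** SAP 7.5 opens with a pooling rule for Part B: "the PK data of ALN-GO1 from both the blinded and open-label portion will be combined at each dose level". Two display rules follow. For tables, "Plasma and urine PK concentration data of ALN-GO1 will be summarized at each scheduled time point by dose level". For figures, "Mean plasma concentrations of ALN-GO1 versus nominal time will be plotted by dose level and study day on both linear scale and semi-logarithm scale", with a further set of plots split by ADA status. Neither rule names the regimen.

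Study day is a defined term. SAP 4.3 gives "Study day = Date of assessment – date of first dose of study drug + 1" for assessments after dosing starts. Study drug includes placebo: SAP 4.2.1 defines its set as those "who received at least 1 dose of study drug (placebo or ALN-GO1"). SAP 7.2 treats the two clocks as different variables, since Part B listings must carry "study day relative to first dose date of study drug, and study day relative to first dose of ALN-GO1". SAP 7.2.2 moves the open-label data of former placebo patients onto the ALN-GO1 clock, but names only Safety and PD data.

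The PK parameter paragraph of SAP 7.5 uses the ALN-GO1 clock for every Part B summary, for example "multiple doses on Day 85 relative to ALN-GO1 dosing (Part B quarterly cohorts only"), and presents results by regimen and dose level.

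**The concern.** One section runs on two clocks. Parameters are grouped by day since the first ALN-GO1 dose. Concentrations are grouped by a term that, as defined, starts at the placebo dose for crossover patients. The scheduled time points used for the tables do not help, because Protocol Tables 11 and 12 index them by study day too.

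The mean curves are where a reader looks to compare the first dose with repeat doses. If they follow the defined term, a curve read as the second quarterly dose includes a patient receiving a first dose, and the first-dose curve omits that patient. In monthly cohorts the pooling that the section promises does not happen. In the ADA-split plots, a patient at a first ALN-GO1 dose would appear in the repeat-dose panel. Anyone comparing the curves with the parameter tables would find different patient counts under the same day label.

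**Working it through.** **Inputs.**
- Cohort size and allocation: 4 patients, 3:1 (SAP 3.1.2).
- Quarterly dosing: patients randomized to ALN-GO1 receive it on Study Days 1 and 85; the placebo patient receives a first ALN-GO1 dose on Study Day 85 (Protocol 4.7.2).
- Monthly dosing: Study Days 1, 29 and 57 for patients randomized to ALN-GO1; Study Days 85, 113 and 141 for crossover patients (SAP 7.4.2).
- Sampling: Protocol Table 12 has one Day 85 profile for all quarterly patients, not split by original arm. Protocol Table 11 lists the monthly crossover profiles separately, from Day 85 on. The only Day 85 PK sample for monthly patients randomized to ALN-GO1 is a single draw at any time during the visit.

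**Step 1. Reproduce the plan's own counts.** 4 × 3/4 = 3 and 4 × 1/4 = 1. This matches the quarterly by-visit shell in SAP 7.2.3 (2-doses N=3, 1-dose N=1, combined N=4). Two cohorts give 6, 2 and 8, which also match.

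**Step 2. Convert the clocks.** For a crossover patient, ALN-GO1-relative day = study day − 85 + 1 = study day − 84. So 85 becomes 1, 113 becomes 29 and 141 becomes 57. For a patient randomized to ALN-GO1 the two clocks agree.

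**Step 3. Group the dosing profiles of one unexpanded cohort.**

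| Regimen | Day label | By study day (SAP 4.3) | By ALN-GO1-relative day |
|---|---|---|---|
| Quarterly | 1 | n=3, first doses | n=4, first doses |
| Quarterly | 85 | n=4: 3 second doses, 1 first dose | n=3, second doses |
| Monthly | 1 | n=3, dose 1 | n=4, dose 1 |
| Monthly | 29 | n=3, dose 2 | n=4, dose 2 |
| Monthly | 57 | n=3, dose 3 | n=4, dose 3 |
| Monthly | 85, 113, 141 | n=1 each: crossover doses 1, 2, 3 | no dosing profile |

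The right-hand column is the grouping already used for PK parameters.

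**Step 4. Expanded cohort.** Up to 4 added patients all receive ALN-GO1 (Protocol 4.1.2), so 3 + 4 = 7 patients have second doses and 1 has a first dose. The misplaced share of the quarterly Day 85 mean falls from 1/4 to 1/8.

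**Step 5. Effect on the mean.** Let R be the ratio of second-dose to first-dose concentration. The documents give no value. If the crossover patient resembles the others at first dose, the mixed mean is (3R+1)/4 of the first-dose level, and its relative departure from the second-dose mean is (1−R)/(4R). That is +6.3% at R=0.8, 0% at R=1, −5.0% at R=1.25, −8.3% at R=1.5 and −12.5% at R=2. With 1 in 8 the departure is (1−R)/(8R), half as large.

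**Step 6. What the documents suggest about R.** The Amendment 1 rationale dropped the Day 141 PK sample for monthly patients randomized to ALN-GO1 because no measurable drug was expected. Day 141 is 141 − 57 = 84 days after their last dose. The quarterly interval is also 85 − 1 = 84 days. The current Tables 2 and 11 still have no such sample, and Protocol 1.5 does not expect significant extra-hepatic exposure through accumulation. This points to R near 1.

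**The case against.** The strongest reply is that the authors probably meant the ALN-GO1 clock. The strict reading leaves nothing to pool in monthly cohorts and so defeats the section's opening rule. The next paragraph uses the ALN-GO1 clock throughout. The section's last sentence lists those same aligned parameters by plain study day, so the term is used loosely. This is fair as to intent, but the concentration sentences do not say it. A programmer who follows the defined term reaches the wrong grouping, and the only realignment rule omits PK.

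Table and figure formats are left to a separate programming specification (SAP 8.2), which is not among the documents reviewed and may already fix the day variable. That stands as a caveat; the SAP should still state the rule.

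It is also fair that little depends on this numerically. The study is descriptive, without hypothesis tests. First-dose and repeat-dose exposure can be read from correctly grouped PK parameters. Individual concentration plots and full listings are planned, so no data are lost. All of this stands, and it limits the point to labelling and patient counts.

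**Conclusion.** The point holds for the Part B concentration tables and mean plots in SAP 7.5, including those by ADA status. Read as defined, they mislabel dose number, leave monthly crossover profiles unpooled, and disagree with the parameter summaries on who is in each group. Because regimen is not named, a Day 85 display could also mix regimens if a monthly and a quarterly cohort shared a dose level; the documents do not say that this will happen.

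The counts assume an unexpanded 4-patient cohort with complete dosing and sampling, and the SAP 4.3 meaning of study day.

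A reader might infer three stronger things that the documents do not support:
- **That the PK parameter endpoints are affected.** They are not: SAP 7.5 ties every Part B parameter summary to ALN-GO1 dosing.
- **That SAP 6.2.2 has the same fault**, because it gives "Day 1 and Day 85 for quarterly dose cohorts" without saying relative to what. Its sentence attaches those days to doses of ALN-GO1. A placebo patient has no ALN-GO1 dose on Study Day 1, so only the ALN-GO1 clock makes sense there.
- **That the curves would materially hide accumulation.** This needs R well above 1, and the stated expectation of no measurable drug at 84 days points the other way. Bias in the means is probably small, and it is zero at R=1.

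**What to change.** In SAP 7.5, state that all Part B concentration summaries and plots, including those by ADA status, use the day relative to the first dose of ALN-GO1 and are presented by regimen and dose level, as the PK parameter paragraph already does. In SAP 7.2.2, add PK to the data realigned for patients first randomized to placebo. Check that the programming specification uses the same day variable. SAP 6.2.2 needs no change.

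The cost is SAP wording only. The relative-day variable is already defined in SAP 7.2.2 and required for Part B listings by SAP 7.2. Sampling, visits and data collection do not change.

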7.6 Pharmacodynamic and Exploratory Analyses

Pharmacodynamic parameters will be measured from blood and urine samples collected at times outlined in the Schedule of Assessments in both Part A and Part B. PD analyses will be based on the Pharmacodynamic Analysis Sets.

24-hour urine oxalate content corrected for BSA will be calculated as:

[24-hour urine oxalate in mmol/L]*[24-hour urine volume recorded in CRF in ml] /(1000 ml per L)*24hours/[actual collection time calculated from CRF in hours] *1.73/[patient BSA]

Where patient BSA will be calculated as:

Patient BSA = sqrt([mean height in cm] *[weight in kg]/3600).

24-hour urine creatinine clearance corrected for BSA will be calculated as:

[24-hour urine creatinine concentration in mg/dl]*[24-hour urine volume recorded in CRF in ml]

/[Plasma creatinine in mg/dl]/[actual collection time calculated from CRF in minutes] *1.73/[patient BSA]24-hour urine oxalate/creatinine ratio will be calculated as:

24-hour urine oxalate concentration (mg/L) /24-hour urine creatinine concentration (mg/dL)/10.

For Part A and Part B, the mean and standard error of actual values and changes from baseline in plasma and urine glycolate will be plotted over time by ALN-GO1 dose level and placebo. In

addition, plots will be provided for plasma and urine glycolate of individual subjects by dose level of ALN-GO1 and placebo.

For Part B, the mean and standard error of actual values and changes from baseline in urinary oxalate per 24-hour urine collection and urinary creatinine per 24-hour urine collection will be plotted over time. In addition, the plots will be presented separately by ADA status. Plasma glycolate concentration and oxalate/creatinine ratio will be plotted in the same manner. For patients randomized to placebo, figures will include PD measurements up to the first dose of open-label study drug.

For other PD variables in Part A and B, descriptive statistics will be provided for actual results, change from baseline, and percent change from baseline. For Part B, the PD summaries will be presented according to the data display specification in Section 7.2.3.For Part A and Part B, Cmax and AUCt of plasma glycolate will be presented with descriptive statistics and percent coefficient of variation [%CV]) by regimen and ascending dose level and placebo presented first.

In Part A and Part B, all PD data will be listed by regimen, dose, ADA status (Part B only) and subject/patient.

7.7 Immunogenicity Analysis

For Part A and Part B, results from tests for antidrug antibodies will be listed by subject in the order of ascending ALN-GO1 dose and placebo for the Safety Analysis Sets.

8 GENERAL INFORMATION

8.1 Statistical Software

The creation of analysis datasets and statistical analyses will be done using SAS® version 9.3 or higher. The Medpace standard operating procedures (Medpace documents) will be followed for the validation of all SAS programs and outputs. Pharmacokinetic parameters will be derived at Alnylam Pharmaceuticals using Phoenix WinNonlin software Version 7.0 or higher.

8.2 Format of Tables, Listings, and Figures

The format of tables, listings, and figures will be described in a stand-alone programming specifications document and will be finalized before database lock for the study.

9 CHANGES FROM THE PROTOCOL SPECIFIED STATISTICAL ANALYSIS

No changes have been issued or planned.

